9.2.2 Laboratory Evaluations

Samples for laboratory assays will be sent to a central laboratory for analysis. Detailed instructions for the collection, processing, and shipment of laboratory samples will be provided by the Sponsor and the central laboratory. The Investigator is responsible for reviewing laboratory results for clinical significance.

The following laboratory evaluations will be conducted during the course of the study:

- **Pregnancy test:** A serum pregnancy test will be performed at SV2 for females of childbearing potential. Additional serum or local urine pregnancy tests may be conducted throughout the study in sufficient number, as determined by the Investigator or required by local regulations, to establish the absence of pregnancy during the study. The SV2 results must be available and must be negative before the subject takes the first dose of study medication.
- **Complete Blood Count (CBC):** A CBC with differential will be performed at Baseline and twice annually at Weeks 28, 52, 76, 104, 128, 156, 180, 208. At all other noted visits in [Appendix A: Schedule of Activities](#), including SV1 and SV2, a CBC without differential will be performed. The CBC with differential will include: Hb, hematocrit, RBCs, mean corpuscular volume (MCV), mean corpuscular hemoglobin (MCH), mean corpuscular hemoglobin concentration (MCHC), red cell distribution width (RDW), white blood cell (WBC) count with differential (neutrophils, lymphocytes, monocytes, eosinophils, basophils), and platelets.

Hemoglobin assessed by central laboratory CBC will be used for evaluations of efficacy and safety. Hemoglobin levels assessed by HemoCue should be used for dose adjustments, as

described in [Section 8.4.4, Dosing and Dose Adjustment Guidelines](#). If the Investigator has an immediate clinical concern about a subject's HemoCue value, the Investigator may use clinical judgement and repeat the HemoCue Hb, use local lab values or wait for central lab results. The test method utilized to inform the treatment decision must be recorded in the source.

For eligibility purposes, one retest for Hb may be performed during the screening window. The average of 2 Hb values measured by the central laboratory during Screening (SV1, SV2, or retest) must be <10.0 g/dL. Refer to [Sections 7.4.1, Retesting](#) and [7.4.2, Rescreening](#) for further details regarding repeating laboratory measurements during the Screening period.

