Point of care Hb: Using HemoCue[®], Hb will be monitored throughout the study to determine if the dose of study medication (vadadustat or darbepoetin alfa) will be adjusted, interrupted, or maintained as described in [Section 8.4.4, Dosing and Dose Adjustment Guidelines](#).

- Reticulocyte count: An automated reticulocyte count (both absolute and percent) will be performed at Baseline and at Weeks 4, 12, 28, and 52.
- Coagulation tests: Blood samples will be drawn at Baseline to assess the prothrombin time (PT), partial thromboplastin time (PTT), and international normalized ratio (INR).
- Folate and Vitamin B₁₂: Blood sample will be drawn at SV1 to assess the folate and Vitamin B₁₂ levels.
- Urine albumin-to-creatinine ratio (uACR): A random urine spot sample should be collected at the investigative site during the Baseline, Weeks 28, 52, 104, 156, 208 and EOT to assess the uACR. Subjects should refrain from heavy exercise 24 hours before the test.
- C-reactive protein (CRP): A blood sample for CRP will be collected at Baseline, Weeks 28, 52, 104, 156, and EOT.
- Serum Chemistry: Blood samples to assess serum chemistry will be collected at SV1, Baseline, and twice annually at Weeks 28, 52, 76, 104, 128, 156, 180, 208, EOT. At all other noted visits in [Appendix A: Schedule of Activities](#), serum creatinine and eGFR will be performed only at Weeks 4, 8, 12, 20, 36, 44. The serum chemistry will include the following assays: sodium, potassium, bicarbonate, chloride, calcium, magnesium, phosphorus, glucose, creatinine, blood urea nitrogen (BUN), creatine phosphokinase (CPK), uric acid, albumin, total protein, and eGFR calculation.

Note: When a $\geq 50\%$ decline in eGFR from the Baseline value is observed, a repeat central laboratory measure should be performed within 30 to 60 days.

- Liver Function Tests: Blood samples to assess liver function will be collected at SV1, Baseline, Weeks 4, 8, 12, 16, 20, 24, 28, 36, 44, 52, 64, 76, 88, 104, 116, 128, 140, 156, 168, 180, 192, 208, and EOT. Liver function tests will include: total bilirubin, alkaline phosphatase, ALT/SGPT, AST/SGOT, and lactate dehydrogenase (LDH).
- Iron indices: Blood samples to assess the iron indices will be collected at SV1, Baseline, Weeks 4, 8, 12, 20, 28, 36, 44, 52, 64, 76, 88, 104, 116, 128, 140, 156, 168, 180, 192, 208, and EOT. Assessments will include the following indices: ferritin, iron, TIBC, and TSAT.

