9.4 Study Medication Stopping Rules

Study medication must be permanently discontinued if a subject meets one of the criteria in Table 2 below

Table 2. Study Medication Stopping Rules

ALT or AST >3x ULN and total bilirubin >2x ULN	Permanently Discontinue Treatment
ALT or AST >3x ULN and INR >1.5	Permanently Discontinue Treatment
ALT or AST >8x ULN	Permanently Discontinue Treatment
ALT or AST remains >5x ULN over 2 weeks *	Permanently Discontinue Treatment

ALT or AST >3x ULN with symptoms including e.g., fatigue, nausea, vomiting, right upper quadrant pain, fever, rash or eosinophilia	Permanently Discontinue Treatment
--	-----------------------------------

* Re-challenge generally should be avoided with ALT or AST >5 times ULN unless there are no other good therapeutic options.

ALT: alanine transferase; AST: asparagine transferase; INR: international normalized ratio; ULN: upper limit of normal

See Section 10.1.1, Adverse Events for reporting requirements related to a subject being permanently discontinued based on meeting the laboratory abnormalities list above in [Table 2](#).

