If new elevations in ALT or AST >3 times ULN, **without** an elevation of total serum bilirubin >2 times ULN are identified, the following steps are to be taken:

- Temporary discontinuation of Investigational Medicinal Product (IMP);
- Repeat testing of ALT, AST, ALP, and total bilirubin, should be completed within 48 to 72 hours to confirm the abnormalities and to determine trend;
- IMP should not be resumed until monitoring indicates abnormalities have resolved or have stabilized.

Details on the management of subjects with other ALT and AST abnormalities are further described in [Section 9.4, Study Medication Stopping Rules](#).

Worsening of Anemia – In this study, it is possible that some subjects may experience a worsening of anemia. As the primary endpoint of this study assesses Hb response, worsening of anemia is captured as part of this efficacy parameter. Worsening of anemia should not be

considered an AE unless the worsening of anemia is associated with a cause *other than* the subject's CKD.

Transplantation – During this long-term study, it is anticipated that some subjects may receive a kidney transplant. These events will not be recorded as AEs. Subjects will discontinue study medication for receipt of a kidney, other solid organ, hematopoietic stem cell or bone marrow transplant and should continue with the Schedule of Activities and safety assessments as described in [Section 7.5.5.2, Permanent Discontinuation of Study Medication](#).

Malignancy – During this long-term study, some subjects may develop a newly diagnosed malignancy or a recurrence of a malignancy. At the discretion of the Investigator, these subjects may continue study medication (vadadustat or darbepoetin alfa). For reporting of adverse events of malignancy, see [Section 10.1.2 Serious Adverse Events](#).

Renal-Related Events - Some subjects will experience a progression of their CKD over the course of this study as part of the natural course of the disease. In addition, the study population is prone to experience acute, transient loss of kidney function of different etiologies, sometimes concomitantly complicated by progression of CKD.

To ensure consistent reporting of renal events, the following guidelines are to be used when reporting a renal-related AE:

- The following situations **should always be reported as SAEs** with seriousness criterion “medically important,” if no other seriousness criteria are met (see Section 10.1.2, Serious Adverse Events):

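### A mandatory liver stopping criterion depends on INR, but no required test after Baseline measures INR, and no INR result is required before drug is resumed

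*Protocol*

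**What the plan says.** Section 9.4, Table 2, lists five liver criteria. Meeting any one of them makes permanent discontinuation mandatory. One is "ALT or AST >3x ULN and INR >1.5"; the synopsis repeats it. Another is "ALT or AST >3x ULN with symptoms including e.g., fatigue, nausea, vomiting, right upper quadrant pain, fever, rash or eosinophilia". A footnote adds: "Re-challenge generally should be avoided with ALT or AST >5 times ULN unless there are no other good therapeutic options".

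On measurement, Section 9.2.2 says of coagulation: "Blood samples will be drawn at Baseline to assess the prothrombin time (PT), partial thromboplastin time (PTT), and international normalized ratio (INR". Section 9.3.4 and Appendix A agree, with a single mark in the Baseline column. The scheduled liver panel has no INR: "Liver function tests will include: total bilirubin, alkaline phosphatase, ALT/SGPT, AST/SGOT, and lactate dehydrogenase (LDH". For the differential: "A CBC with differential will be performed at Baseline and twice annually at Weeks 28, 52, 76, 104, 128, 156, 180, 208".

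Section 10.1.1 covers a new ALT or AST above 3x ULN without bilirubin above 2x ULN. Study medication is stopped temporarily. Then: "Repeat testing of ALT, AST, ALP, and total bilirubin, should be completed within 48 to 72 hours". On restart: "IMP should not be resumed until monitoring indicates abnormalities have resolved or have stabilized". The section next refers the reader to Section 9.4 for other ALT and AST abnormalities. Section 9.3.11 lets the investigator add other medically warranted procedures at an unscheduled visit.

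**The concern.** A stopping rule can be applied only if the quantity in it is measured. Routine INR at every visit is not needed, since the criterion matters only once ALT or AST is above 3x ULN. The work-up triggered at that point is where INR belongs, and it is not there. Subjects with bilirubin above 2x ULN already stop permanently under a different criterion. Those sent through the temporary-stop pathway are therefore the ones in whom INR can turn a temporary stop into a permanent one.

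What is at stake is the restart decision. A subject with an unmeasured INR above 1.5 could be put back on drug although Section 9.4 requires a permanent stop. Stopping rules and safety laboratory tests belong in the protocol, so this is not something a protocol would normally leave to the SAP.

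**Working it through.** No sample size, power or error rate is involved. The check is a cross-reading of Table 2 against the tests that the Amendment 7 protocol requires.

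**Required post-Baseline measurements of each laboratory item in Table 2**

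| Item | Source | Required post-Baseline | In 48 to 72 hour repeat panel |
|---|---|---|---|
| ALT, AST, total bilirubin | 9.2.2 | 22 scheduled weeks, plus EOT | Yes |
| Eosinophils (CBC differential) | 9.2.2 | 8 scheduled weeks | No |
| INR | 9.2.2, 9.3.4 to 9.3.10, Appendix A | 0 | No |

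The 22 liver-test weeks are 4, 8, 12, 16, 20, 24, 28, 36, 44, 52 (10), then 64, 76, 88, 104 (4), then 116, 128, 140, 156 (4), then 168, 180, 192, 208 (4): 10 + 4 + 4 + 4 = 22. The 8 differential weeks are 28, 52, 76, 104, 128, 156, 180 and 208, all of them liver-test weeks. So 22 − 8 = 14 liver-test weeks have no differential. INR is required once per subject, at Baseline.

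**The repeat panel** contains four analytes: ALT, AST, ALP and total bilirubin. Neither INR nor a differential is among them.

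**Who is left without a check.** Start from ALT or AST above 3x ULN and remove those whom another Table 2 criterion stops permanently:

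1. Remove bilirubin above 2x ULN.
2. Remove ALT or AST above 8x ULN.
3. Remove ALT or AST remaining above 5x ULN over 2 weeks.
4. Remove those with symptoms or eosinophilia.

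Two bands remain: more than 3x and up to 5x ULN for any duration, and more than 5x and up to 8x ULN not persisting over 2 weeks. In the second band the footnote already discourages re-challenge. The first band is where the missing INR matters most. Step 4 is itself not fully assured by required tests, because the repeat panel does not look for eosinophilia.

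**Origin.** Appendix F and the Amendment 7 table of changes show that Section 9.4 was added, and the repeat-testing text edited, in that amendment. The listed changes do not include Section 9.2.2 or Appendix A. This suggests the new criterion was not carried through to the test schedule; that is an inference, not something the document states.

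**The case against.** A reader might infer that Section 10.1.1 permits a restart that Section 9.4 forbids, so that a site following one section exactly would breach the other. The text does not support that. Section 10.1.1 says when drug must not yet be resumed, which is a necessary condition and not a sufficient one. It then points to Section 9.4, as does Section 7.5.5. An investigator bound by a mandatory rule has reason to check INR. What is missing is an explicit instruction.

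A reader might also infer that INR is the only Table 2 item missing at the restart decision. It is the only laboratory item with no required post-Baseline measurement at all, but eosinophilia is also absent from the repeat panel.

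Several safeguards narrow the gap:

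- Drug is withheld during the work-up.
- Elevations with no other identified cause are reported as SAEs within 24 hours. (The condition about other causes is legible in the Amendment 7 table of changes.)
- SAE subjects are monitored until the event resolves or stabilizes (Section 10.3.3).
- Interruptions longer than 60 days need Medical Monitor contact before restart (Section 7.5.5.1).
- The symptom criterion is open-ended and includes fatigue, which the protocol also names as a symptom of anemia, so some of these subjects will stop without an INR.
- Central-laboratory instructions are in documents not shown; whether they include a reflex INR is unknown.

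All of this stands and limits the size of the point. None of the steps in the protocol requires an INR.

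**Conclusion.** The point holds as a gap in the required work-up, not as a conflict between sections. One of the five mandatory criteria cannot be evaluated from any required post-Baseline test, and whether it is checked rests on investigator discretion. The consequence is confined to the restart decision, mainly in asymptomatic subjects at more than 3x and up to 5x ULN with bilirubin not above 2x ULN. How many there would be cannot be derived from the document. Efficacy endpoints and power are unaffected. It should be fixed because it concerns a mandatory liver-safety rule and the remedy is small. The conclusion assumes that no laboratory manual outside the protocol already requires a reflex INR.

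**What to change.** In Section 10.1.1, add PT/INR and a CBC differential to the 48 to 72 hour repeat panel, and require the results to be checked against Table 2 before drug is resumed. List both as triggered tests in Section 9.2.2 and Appendix A. Table 2 and its synopsis copy need no change.

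Leave the 1.5 threshold as it is. A special reading of INR for anticoagulated subjects would alter the stopping criterion itself and is not needed to close this gap.

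The cost is one extra tube for PT/INR, plus the CBC sample for the differential, on a draw already required and only in subjects who trigger the pathway. Restart also waits a short time for the results. The downside is that anticoagulant use is not an exclusion: Section 7.3 excludes only DVT or PE within 12 weeks before randomization, and Appendix F states that chronic anticoagulation for older events is acceptable. Some anticoagulated subjects will therefore meet the existing criterion once INR is measured.

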10 ADVERSE EVENTS

10.1 Definitions

10.1.1 Adverse Events

For the purposes of this study, an AE is any untoward medical occurrence (including an abnormal laboratory finding) that occurs in the protocol-specified AE reporting period; the event does not necessarily have a causal relationship with that treatment or usage.

An AE includes medical conditions, signs, and symptoms not previously observed in the subject that emerge during the protocol-specified AE reporting period, including signs or symptoms associated with pre-existing underlying conditions that were not present prior to the AE reporting period.

Adverse events therefore include the following:

- All AEs, whether suspected to be causally related to study medication or otherwise
- All AEs secondary to any medication overdose, medication error, abuse, withdrawal, sensitivity, or toxicity
- Illnesses apparently unrelated to study medication, including the worsening of a pre-existing illness (see paragraph below on Pre-existing Conditions)
- Injury or accidents. Note that if a medical condition is known to have caused the injury or accident (eg, a fall secondary to dizziness), the medical condition (dizziness) and the accident (fall) should be reported as 2 separate AEs.
- Abnormalities in physiological testing or physical examination findings that require clinical intervention or further investigation (beyond ordering a repeat [confirmatory] test)
- Laboratory abnormalities that require clinical intervention or further investigation (beyond ordering a repeat [confirmatory] test) unless they are associated with an already reported clinical event. Laboratory abnormalities associated with a clinical event reported as an AE (eg, elevated liver enzymes in a subject with jaundice) should be described under ‘Comments’ on the report of the clinical event rather than reported as separate AEs.

The following guidelines are to be used when reporting AEs for this study:

Medical Diagnoses – Whenever possible, a medical diagnosis term should be used to report AEs instead of signs and symptoms due to a common etiology, as determined by qualified medical study staff. For example, pneumonia should be the reported AE term, instead of fever or dyspnea, when the diagnosis has been established. Signs and symptoms should be reported as

event terms only when the medical diagnosis remains unknown and revised to a medical diagnosis term once it has been established.

Procedures – Diagnostic and therapeutic non-invasive and invasive procedures, such as surgery, should not be reported as AEs. However, the medical condition for which the procedure was performed should be reported if it meets the definition of an AE. For example, an acute appendicitis that begins during the AE reporting period should be reported as the AE and the resulting appendectomy noted under ‘Comments’.

Pre-planned therapeutic procedures not associated with a new medical condition or worsening pre-existing condition should not be reported as AEs (with the exception of kidney transplant, see below).

Pre-existing Conditions – In this study, a pre-existing condition (ie, a disorder present before the AE reporting period started and noted on the pretreatment medical history/physical examination form) should not be reported as an AE unless the condition worsens or episodes increase in frequency during the AE reporting period.

Abnormal Test Findings – All laboratory test results will be reviewed by the Investigator. The Investigator will utilize his/her judgment in determining if out of range laboratory values are clinically significant and will denote this using the abbreviation “CS” on the laboratory report for source documentation. Laboratory tests that are labeled as clinically significant should be reported as AEs, either separately or as part of a description of a symptomatic AE. If there are significant changes in a laboratory report from a previous visit that are determined to be clinically significant, these should also be reported as AEs. Any abnormal laboratory value which requires treatment or further diagnostic testing and/or results in discontinuation from study should be reported as an AE. An expected laboratory abnormality from a condition that is part of the medical history is not considered clinically significant for the purposes of the study unless it represents a worsening of the condition.

Abnormalities in ALT, AST and Total Bilirubin - Abnormalities in ALT, AST and Total Bilirubin should be reported to the Sponsor’s Medical Monitor or CRO designee within 24 hours of awareness as SAE with “medical significance” criteria selected, if the following conditions are met:

- New elevation in ALT or AST > 3 times ULN, with or without an elevation of total serum bilirubin >2 times ULN; AND

If new elevations in ALT or AST >3 times ULN, **without** an elevation of total serum bilirubin >2 times ULN are identified, the following steps are to be taken:

- Temporary discontinuation of Investigational Medicinal Product (IMP);
- Repeat testing of ALT, AST, ALP, and total bilirubin, should be completed within 48 to 72 hours to confirm the abnormalities and to determine trend;
- IMP should not be resumed until monitoring indicates abnormalities have resolved or have stabilized.

Details on the management of subjects with other ALT and AST abnormalities are further described in [Section 9.4, Study Medication Stopping Rules](#).

Worsening of Anemia – In this study, it is possible that some subjects may experience a worsening of anemia. As the primary endpoint of this study assesses Hb response, worsening of anemia is captured as part of this efficacy parameter. Worsening of anemia should not be

considered an AE unless the worsening of anemia is associated with a cause *other than* the subject's CKD.

Transplantation – During this long-term study, it is anticipated that some subjects may receive a kidney transplant. These events will not be recorded as AEs. Subjects will discontinue study medication for receipt of a kidney, other solid organ, hematopoietic stem cell or bone marrow transplant and should continue with the Schedule of Activities and safety assessments as described in [Section 7.5.5.2, Permanent Discontinuation of Study Medication](#).

Malignancy – During this long-term study, some subjects may develop a newly diagnosed malignancy or a recurrence of a malignancy. At the discretion of the Investigator, these subjects may continue study medication (vadadustat or darbepoetin alfa). For reporting of adverse events of malignancy, see [Section 10.1.2 Serious Adverse Events](#).

Renal-Related Events - Some subjects will experience a progression of their CKD over the course of this study as part of the natural course of the disease. In addition, the study population is prone to experience acute, transient loss of kidney function of different etiologies, sometimes concomitantly complicated by progression of CKD.

To ensure consistent reporting of renal events, the following guidelines are to be used when reporting a renal-related AE:

- The following situations **should always be reported as SAEs** with seriousness criterion “medically important,” if no other seriousness criteria are met (see Section 10.1.2, Serious Adverse Events):
 - **Progression of CKD leading to chronic dialysis**: When a subject undergoes transition to chronic maintenance dialysis, an SAE should be reported using the verbatim term of “end-stage renal disease” with the outcome denoted as recovered with sequelae of chronic dialysis.
 - **Any medical event requiring transient acute dialysis**: When a subject undergoes transient acute dialysis, an SAE should be reported using the verbatim term reflecting the indication for the dialysis. Examples of verbatim AE terms include: hyperkalemia, volume overload, acute kidney injury, and uremia.
 - **Kidney transplantation**: When a subject receives a kidney transplant, an SAE should be reported using the verbatim term “Progression of CKD,” with the outcome denoted as recovered with sequelae of “kidney transplant.”
- The following situations will be **reported as SAEs if they meet seriousness criteria** (see Section 10.1.2, Serious Adverse Events); otherwise, they should be reported as AEs:
 - **Acute kidney injury not requiring dialysis** – The reported AE term should reflect the etiology for the impairment of the renal function. Non-specific AE terms such as “Decreased eGFR” or “Increased creatinine” should be avoided whenever the underlying etiology is known.
 - Examples of verbatim AE terms for prerenal impairment include: hypovolemia, hepatorenal syndrome, and heart failure
 - Examples of verbatim AE terms for intrarenal impairment include: acute tubular necrosis, acute interstitial nephritis, and glomerulonephritis

- Examples of verbatim AE terms for postrenal impairment include: hydronephrosis, pelvicaliectasis, and urinary tract obstruction
- Progression of CKD not requiring dialysis – If permanent loss of renal function due to underlying CKD has occurred, the reported AE term should reflect the underlying etiology. Non-specific terms such as “Decreased eGFR,” “Increased creatinine,” or “Worsening CKD” should be avoided whenever the underlying etiology is known. Examples of verbatim AE terms include: worsening lupus nephritis, worsening diabetic kidney disease, and worsening glomerulonephritis.
- Medical conditions related to CKD that occur without acute kidney injury or progression of CKD – If there is no decline in kidney function, the medical complication of CKD itself should be reported. AE terms such as “Progression of CKD” or “Acute Kidney Injury,” should be avoided when there is no decline in kidney function. Examples of AE terms include: edema and hyperkalemia.

